A detailed therapist manual outlines procedures for every contact session with participants, and for participant issues that could represent risk, the manual outlines responses to minor, moderate, and severe side effects with first-line, second-line, and indications to call the PI by phone for urgent or emergent issues. Research staff including the investigators and PI will be available to evaluate any change in a participant's condition. Participants will be asked to contact us at any time if any unpleasant effects occur and will be contacted by study staff at least weekly during study participation. A study physician will be at the study site on medication dosing days to manage psychiatric emergencies.

Synthesized psilocybin: Reviews of the drug and the literature indicate that the physiological and psychological effects are transient. The patient will be monitored at all times by trained research and/or medical staff. The study medical doctors and nursing staff who are trained in dealing with drug challenge studies (such as ketamine, psilocybin, yohimbine, and various cannabis compounds) will remain in attendance during the entire session. Participants will be asked to remain on the CNRU until effects wear off. Procedures will be immediately stopped if participants request or if they are exhibiting significant distress. To minimize risk associated with synthesized psilocybin, participants will undergo a thorough screening for contraindicated psychological conditions or interacting medications. Dosing with psilocybin must be performed in a setting that minimizes distraction and interruption, and the participant must be attended following the dose by research staff trained in providing reassurance and a safe environment until the effects of the single dose have dissipated.

The PI may prescribe a designated rescue medication in the event of symptoms that require it during or after the medication dosing session. Rescue medications may be a benzodiazepine, zolpidem, or other anxiolytic or sedative according to the physician's clinical judgment.

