After the FDA has approved the content of the protocol, the psilocybin will be provided by the Usona Institute, Inc., [name], who will provide this iforefinas a supplement to this IND application. The Usona Institute utilizes a contract manufacturing organization (CMO) to manufacture GMP psilocybin, and the CMO is Almac Pharma Services Limited, [name]. Using a 222 DEA form, the psilocybin will be shipped to [name] to be stored in DEA safe located in the Investigational Pharmacy at Harborview Medical Center. To safeguard the psilocybin, a special storage safe will be approved by DEA to store only the psilocybin. Designated staff will be the only personnel with access to the psilocybin. Both the active and placebo will be prepared by designated study staff by a compounding process. The UW Investigational Pharmacy (IDS) will store and track the accountability of the psilocybin. A log of the psilocybin accountability, compounding, and release to the study team will be kept by the designated IDS staff. This will provide strict safeguarding and accounting of the agent both for internal and external regulatory agencies. The sponsor-investigator will be the DEA Schedule 1 license holder and will dispense the drug directly to study participants.

6. Study Procedure and Schedule

This study will use a randomized, placebo-controlled, double-blind design to examine the clinical and neural effects of psilocybin-assisted psychotherapy with either synthesized psilocybin (25 mg) or placebo (niacin 100 mg), given along with non-drug preparatory and integrative psychotherapy sessions. The duration of the randomized study phase is from consent until two weeks after drug administration, which is approximately 6 weeks. The blind will be broken at 4 weeks after measures have been completed, and the participants who received placebo will be offered the option toreceive open-label psilocybin. In addition to the baseline assessments and medical evaluation, the study will consist of atleast two Preparation sessions with the study therapists, the medication dosing session (which will require at least 7 hours), and post-medication session Integration sessions, starting the following morning after the medication dosing session and continuing at 2 weeks, 3 weeks, and 4 weeks post-medication. These integration sessions may be conducted by secure videoconference.

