6.2.3. Medication Dosing session (Visit 3)

Procedures for psilocybin administration and the conduct of the session will be similar to procedures used in studies with psilocybin conducted at New York University, Johns Hopkins, and Yale. Participants will be instructed to consume a low-fat breakfast before reporting to the clinic room for the psilocybin sessions. Before psilocybin administration, urine pregnancy test will be conducted in females of childbearing potential, and a negative pregnancy test will be required in order to continue in the medication session. Participants and staff will also complete pre-session questionnaires. Before each psilocybin session, study personnel will interview the participant. If the investigator believes that the session is contraindicated, the session will be cancelled or postponed.

Psilocybin will be administered in opaque gelatin capsules with approximately 100 ml water. At least one therapist, under the supervision of the investigators, will be present in the room and available to respond to participants' physical and emotional needs during the full course of the session (at least 7 hours). A physician on the study team will be immediately available via pager or mobile phone for at least 3 hours or until the peak effects of psilocybin have subsided, whichever is longer.

During the session, participants will lie on a couch, wear eyeshades, and listen to a program of music through headphones. The participant will be encouraged to focus her or his attention inward. The eyeshades and music are intended to encourage this inward reflection. Heart rate and blood pressure will be measured pre drug administration, at 30, 60, 90, 120 minutes after drug administration, and then at least hourly until at least 6 hours after drug administration and until drug effects have subsided. Heart rate and blood pressure assessments will be obtained after the participant has been sitting or recumbent for at least 5 minutes. Sessions are expected to last approximately 7 to 10 hours. A sample schedule for the medication dosing session is as follows:

Approximate Time	Procedure or Action
09:00	Urine pregnancy test for females of childbearing potential,
	participant acclimates to environment, completes measures.
09:30	Baseline BP, Pulse, Temp.
	Medication Administration.
	Begin video recording.
10:00	BP, Pulse
10:30	BP, Pulse
11:00	BP, Pulse
11:30	BP, Pulse
12:30	BP, Pulse
13:30	BP, Pulse
14:30	BP, Pulse
15:30	BP, Pulse
16:30	BP Pulse.

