	Assessment for discharge home.

At about the same time of each heart rate/blood pressure measurement, monitors will complete notations in the Medication Day Case Report Form to rate the presence and intensity of behaviors, signs, and reported symptoms, including sleepiness, amount of speech, anxiety, stimulation/arousal,

tearing/crying, nausea/vomiting, yawning, restlessness, feelings of unreality, visual changes, euphoria, and peacefulness. Video and audio recordings will be made throughout the session, as allowed by participants.

Participants will be encouraged to lie comfortably in bed wearing eye shades during the first few hours of the experience and to listen to pre-selected music chosen by the study staff. Two team members will remain with the participants the entire time and beavailable for any processing of intrapsychic material made manifest by the treatment.

If participants experience or report on any adverse effects or if the research staff feelsthat at the end of testing, that the participant has any adverse effects, participants will be asked / required to remain until effects wear off and medically cleared by the PI. Medical assistance will be offered. The investigators will query participants about suicidal ideation or intent during screening, and prior to each psilocybin session. Participants who evidence suicidal ideation or intent will be withdrawn from the study and referred to appropriate psychiatric care.

In the event that participants experience distressing anxious symptoms during the drug session, the clinical personnel in attendance (the principal investigator and team member) will initiate verbal communication designed to reorient and reassure that participant. The occurrence and intensity of anxiety or panic responses can be reduced through providing participants with information on potential drug effects, supervision, and monitoring of participants for the duration of drug effects. The goal in this study is to treat participants undergoing anxiety or panic reactions first by verbal and psychological interventions and using anxiolytic medication only after verbal and psychological interventions have failed, and if participants are endangering themselves or others. Residual symptoms will be addressed during the frequent follow-up psychotherapy visits with the investigators.

At the end of the medication dosing session:

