6.4. Rescue Medications, Treatments, and Procedures

The plan for managing psychiatric emergencies includes:

- A detailed therapist manual, and training for all study therapists on procedures in the manual for handling potential adverse events including agitation, hallucinations, anxiety, and other intense psychological reactions.
- The two-person therapist team that will be with the participant for the entire medication dosing session will include a licensed therapist or physician with training in psychiatric emergencies and adverse effects of psychedelics.
- A psychiatrist team member will be involved in screening and evaluation of all participants.
- A physician with training in psychiatric emergencies and adverse effects of psychedelics will be immediately available on site for the medication dosing days.
- A psychiatrist team member will be immediately available to assess any participant noted by study staff to have a significant change in mood or suicidality.
- In the event of a psychiatric emergency, the Harborview Medical Center Psychiatry Emergency Services in the next building is available 24 hours a day, with on-site psychiatrists and nurse practitioners.
- The PI may prescribe a designated rescue medication in the event of symptoms that require it during or after the medication dosing session. Study therapists who have performed first-line and second-line interventions (that do not involve medications) will have the ability to contact the PI by phone, who is available to assess patients within 20 min during every medication session. If a patient does have an adverse reaction that requires a rescue medication, participants will be monitored for up to 2 hours beyond the required 6 hour duration of the session. If at the end of that period that participant requires further, [name] (PI) will consult with the attending psychiatrist on call at Harborview Medical Center.

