If participants experience or report on any adverse effects or if the research staff feels that at the end of testing, that the participant has any adverse effects, participants will be able to remain until effects wear off (likely only for a short period) and medical assistance will be offered. Participants will be free to withdraw from the study whenever they wish. In addition, if any participant presents with an adverse reaction to the psychopharmacological agent as reported by them or assessed by a member of the research team, we will discontinue the study and call for medical assistance

6.5. Safety Plan for Suicidality:

During all study visits a study investigator with clinical training will assess the participant's well-being – responses, intent, plan, etc. while administering the C-SSRS (Columbia Suicidality Severity Response Scale). If these procedures result in any serious concerns on the part of the investigator, they will either ask the participant to meet with or call the PI or escort the participant to the

Page 31 Version 1.16, July 18, 2022

emergency room. If necessary, they will also call the participant's treating clinician and/or their emergency contact. As part of the consent, participants are required to designate an emergency contact person and provide their treating clinician's contact information. We will ask the treating clinician for their local plan for such emergencies so the study team can follow this plan should an emergency situation arise.

7. Payments for Participation (Economic Considerations)

Participants will not be paid for their participation. Expenses of participating in the study, such as parking will be covered by the study.

8. Assessment of Safety

- 8.1. Specification of Safety Parameters
- 8.1.1. Definition of Adverse Events (AE)

Adverse events (AEs) are defined any untoward, physical, social, economic, or psychological occurrence affecting human subjects in research. An AE can be any unfavorable or unintended event including abnormal laboratory finding, symptom, reaction, or disease. An AE does not necessarily have a causal relationship with the research, or any risk associated with the research, the research intervention, or the assessment. Adverse events involve subjects only.

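### The post-rescue monitoring window in 6.4 assumes a 6-hour session where section 6 and 6.2.3 set 7 hours or more, and 6.2.3 and 6.4 give different stay rules for the same adverse-effect trigger

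*Combined protocol and SAP*

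**What the plan says.** **Stay rule.** Section 6.2.3 says that, when adverse effects are reported or noticed at the end of testing, "participants will be asked / required to remain until effects wear off and medically cleared by the PI". Section 6.4 opens with almost the same condition but continues "participants will be able to remain until effects wear off (likely only for a short period) and medical assistance will be offered". It names no clearance step, and its next sentence confirms that participants may withdraw at any time. Section 1.3.3.8 uses a third form, in which participants are asked to stay.

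**After a rescue drug.** Section 6.4 says "participants will be monitored for up to 2 hours beyond the required 6 hour duration of the session". If more care is needed at that point, the PI consults the on-call psychiatrist. Section 1.3.3.8 lists a benzodiazepine, zolpidem or another anxiolytic or sedative as possible rescue drugs.

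**Session length.** The opening of section 6 refers to "the medication dosing session (which will require at least 7 hours". Section 6.2.3 repeats that minimum and adds "Sessions are expected to last approximately 7 to 10 hours".

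**Physician access.** Section 6.2.3 asks for a physician "immediately available via pager or mobile phone for at least 3 hours or until the peak effects of psilocybin have subsided", whichever is longer. Section 6.4 has a physician who "will be immediately available on site for the medication dosing days", and 1.3.3.8 says "A study physician will be at the study site on medication dosing days to manage psychiatric emergencies".

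**The concern.** Section 6.4 is where staff would look during an event. Its post-rescue sentence reads as a promise of extra observation, but it starts from a session shorter than the one the protocol requires. It states only an upper limit, and it is not tied to when the rescue drug was given. A participant given a sedative late in the session is therefore guaranteed no observation time by that sentence.

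On staying, one section leans towards obligation with medical clearance and the other offers a choice without it. Staff should not have to decide which governs while a participant still has effects. What is at stake is participant safety and consistent conduct. The primary comparison of MADRS change, the sample size and the power do not depend on any of this.

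**Working it through.** **Inputs**
- Session base 6 h, extension at most 2 h (6.4).
- Session minimum 7 h (section 6; 6.2.3); expected range 7 to 10 h (6.2.3).
- Sample schedule: arrival procedures 09:00, dose 09:30, discharge assessment 16:30 (6.2.3).

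**1. The plan's own figure.** 6 + 2 = 8 h. The 6 h base does not reproduce from the session text: 16:30 − 09:30 = 7 h. The one monitoring period of 6 h is the minimum for vital signs after dosing in 6.2.3, which is probably where the figure came from, but that is not the session length.

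**2. What the window adds to a session of S hours.** Extra = 8 − S, at most.
- S = 7: 1 h
- S = 8: 0 h
- S = 10: 8 − 10 = −2, so nothing

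**3. Sensitivity to the reading**
- 6 h counted from the dose: 09:30 + 8 h = 17:30, which is 1 h after the 16:30 assessment.
- 6 h counted from 09:00: 09:00 + 8 h = 17:00, which is 0.5 h after the assessment and 7.5 h after dosing.
- 2 h added to the real session instead: 7 + 2 = 9 h to 10 + 2 = 12 h.

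One sentence can thus mean an end point anywhere from 7.5 to 12 h. On every reading the minimum is zero, because only a maximum is stated.

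**4. Which anchor to use.** Let t be the hour of the last rescue dose.
- Anchoring to the rescue dose alone, with a 7 h floor, fails for early rescue. At t = 1, max(7, 1 + 2) = 7 h, so the planned extension disappears.
- Using the later of S + 2 and t + 2 keeps it. At S = 7 and t = 1, max(9, 3) = 9 h.
- The second term matters when rescue is given after the session, which 1.3.3.8 and 6.4 allow. As an illustration, S = 7 and t = 8 gives max(9, 10) = 10 h.

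**5. Stay and discharge rules side by side**

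| Place | Obligation | Ends when | Clearance |
|---|---|---|---|
| 6.2.3, adverse effects | asked or required | effects gone and cleared | PI |
| 6.4, adverse effects | optional | effects gone | none stated |
| 6.2.3, end-of-session list | all participants stay | participant and investigator agree impairment is over | investigator |
| 1.3.3.8, holding item | by stated criteria | physician judges it safe | study physician |
| 8.13 | not stated | not stated | PI or designated physician available to clear |

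The first two rows conflict. The last three supply safeguards that 6.4 omits.

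**6. How often the rescue sentence would be used.** Psilocybin sessions: 15 randomised + up to 15 open-label = 30, or 18 + 18 = 36 if all 36 enrolled are randomised equally. Section 1.3.3.8 reports no rescue use for psychological reactions in academic studies since 2000. At an assumed rate of 1% to 5%, the expected number is 0.01 × 30 = 0.3 to 0.05 × 36 = 1.8 sessions.

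**The case against.** The best defence is that the protocol, read whole, already protects discharge. The end-of-session list in 6.2.3 applies to everyone and keeps participants under observation until the investigator agrees they are unimpaired. Section 6.2.3 also continues vital signs until drug effects subside. Section 1.3.3.8 ties discharge to a physician's judgement, although under the overnight-holding item, and 8.13 gives therapists immediate access to a physician who can clear a participant. Silence in 6.4 does not cancel these rules. A therapist manual, not among the documents, may settle the details. Most of this stands, and it limits the severity. It does not make the 6 h figure right or say which stay rule governs.

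Three stronger readings are tempting and should be resisted:
- **A sedated participant is released at 8 h.** The documents do not say so. The end of the window leads to a psychiatric consultation if needed and is not a release time.
- **Physician cover lapses at 12:30, three hours after dosing.** The 3 h in 6.2.3 applies only if peak effects have subsided by then. Sections 1.3.3.8 and 6.4 put a physician on site, and 1.3.3.8 keeps medical and nursing staff in attendance throughout.
- **Section 6.2.3 flatly compels a stay.** It offers asking and requiring as alternatives, so the contrast with 6.4 is real but softer than that.

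Nor does the figure of up to 40% for intense reactions in 1.3.3.8 measure this problem. It counts transient reactions during sessions, and no figure is given for effects still present at the end.

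**Conclusion.** Two inconsistencies hold. The post-rescue window rests on a session length that section 6 and 6.2.3 contradict, so the stated extra monitoring is worth 1 h at most against a 7 h session, nothing from 8 h upward, and has no floor. Sections 6.2.3 and 6.4 also give different stay and clearance instructions for one trigger.

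Severity is low. The remaining safeguards make unsafe discharge unlikely, rescue use should be rare, and no efficacy result changes. The window arithmetic uses only the protocol's own hours; the 0.3 to 1.8 sessions rest on the assumed rescue rate. The conclusion does not depend on that rate, because the text is inconsistent whatever its frequency.

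**What to change.** 1. **Section 6.4, post-rescue sentence.** Require monitoring until the later of two times: 2 hours after the session ends (the session lasting no less than 7 hours) and 2 hours after the last rescue dose. Monitoring then continues until the PI or a designated physician clears the participant. Keep the psychiatrist consultation. The 2 hours is the protocol's own figure made a minimum; the documents do not show that it suits each rescue drug, so the study physicians should confirm it.
2. **Section 6.4, stay rule.** Adopt the 6.2.3 rule, with clearance by the PI or a designated physician as 8.13 already allows. Apply it to effects still present at the end of the session, so that niacin flushing that has passed does not trigger it. State that it overrides neither the right to withdraw nor the holding criteria in 1.3.3.8. The matching sentence in 1.3.3.8 can follow.
3. **Optional.** Bring the pager-or-phone wording in 6.2.3 into line with the on-site physician in 1.3.3.8 and 6.4, as a wording alignment only.

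The cost is a short amendment, a check that the therapist manual agrees, and occasional extra staff time after a rescue dose.

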6.2.4. Integration sessions (Visit 4, 5, and 6)

During the meetings with the study therapists after the medication dosing session, participants will complete questionnaire assessment measures. During visit 4, study therapists will also complete questionnaires retrospectively rating various behaviors and experiences observed on the session day and reported by the participant during the meeting (using the Next-Day Monitor Rating Form), and participants will be asked to discuss the narrative description of their medication session.

The purpose of the integration sessions is to ensure psychological stability after the medication dosing session and provide an opportunity for the participant to discuss thoughts or feelings from the session. These post-medication integration sessions allow time for reflection, meaning-making and psychological change. Audio or video recordings (with coded id number) of this session will be made.

6.2.5. Long-term follow-up

A study therapist who conducted the integration, medication dosing and preparation sessions will contact the participant at 3 months post-psilocybin, and 6 months post-psilocybin

(note that this takes into account participants who receive psilocybin after the primary endpoint measures have been collected in the open label phase of the study (see below). The therapist will have a 30 min phone call or video call with the participant, and the participants will fill out measures using a secure online portal.

6.2.6. Timing and Location of Meetings, Sessions, and Measures.

Although much effort is put in to scheduling participants within the stated time frames, these are only estimates. Variables out of the study team's control (e.g., participant availability, university closings, availability of study rooms, illness) may prevent the scheduling of volunteers within the stated time frame goals. There is no evidence to suggest that the difference in timing of sessions, meetings, and measures will adversely affect the volunteer or the validity of the study. On those occasions when the timing of meetings, sessions or measures deviate substantially from the time frames in the protocol, we will report these as deviations in the Continuing Review.

6.3. Open Label Psilocybin Sessions.

The participants who choose to receive open-label psilocybin will be re-screened after the blind is broken after primary endpoint measures are collected (week 4) to make sure they still meet study criteria. If they are eligible and choose to enroll in the open-label continuation, they may do so, undergoing a psilocybin-assisted session occurring within another seven to 14-day period.

The open-label phase of the study will follow nearly identical procedures to those used in the randomized phase except that a single preparation psychotherapy session will be given (see Schedule below, Study day -1). Participants will be re-assessed on all study measures following the same schedule of the randomized phase.

Participants need not complete any portion of the open-label phase or the several follow up support appointments for their participation in the study to be considered completed.

Data will be collected from all subjects after open-label treatment for descriptive purposes and will be viewed not as part of our primary analysis plan but as part of a secondary analysis examining the impact of PAP on symptoms of depression and burnout.

Schedule for Activities during Open Label Psilocybin Phase										
Purpose	Prep	Medi- cation	Inte- gration	Inte- gration	Inte- gation	1 011011	Follow -up	Follow -up	Follow -up	Follow -up
Study day ('denotes open-label)	-1'	0'	1'	7'	14'	21'	28'	56'	84'	180'
Visit number	V7	V8	V9	V10	V11	V12	V13*	V14*	V15*	V16*
Research activity										
Psychiatric evaluation	Х									
Education re expectations	Х									
Preparation psychotherapy	Х									
Urine screen		Х								
Medication (psilocybin)		Х								
Medication dosing monitoring		Х								
Integration psychotherapy			Х	Х	Х					
Adverse event reporting		Х	X	X	X					
Measures										
Montgomery Asberg Depression	Х		Х	Х	Х	Х	Х	Х	X	
Beck Depression Scale	Х		Х	Х	Х	Х	Х	Х	X	
Stanford Fulfillment Index	Х		X	Х	Х	Х	Х	Х	Χ	
Post-traumatic stress (PCL5)	Х		Х	Х	Х	X	X	X	X	

Page 30 Version 1.16, July 18, 2022

Likelihood to leave job	Х				X					
Self-reported mystical exp		X								
Moral injury symptom scale		X						X		
Psychedelic music questionnaire			X							
Psychological flexibility (AAQII)	Χ				X	X	X	X	X	
Suicidality (C-SSRS)	Χ	X	X	X	X	X	X	X	X	X
Qualitative interview						X				
Adverse events	Х	X	X	X	X	X	X	X	X	

^{*}Note that V13, V14, V15, and V16 are likely to be video or remote visits.

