2.3.2. Secondary Endpoints

- Assess symptoms of depression using the Montgomery-Asberg Depression Rating Scale (MADRS) prior to the primary endpoint at 1 week post psilocybin-assisted psychotherapy vs control psychotherapy.
- Assess symptoms of depression using the MADRS after psilocybin administration (for patients randomized to psilocybin or who receive open-label psilocybin) at 1 week, 4 weeks, 8 weeks, 12 weeks, and 6 months.
- Assess symptoms of burnout using the Stanford Fulfillment Index (SFI) at 4
 weeks post medication administration. We expect at least 50% of participants
 treated with psilocybin to show a reduction in the SFI work exhaustion and
 interpersonal disengagement subscales by at least 25% (from "a lot" to
 "moderately").
- Assess symptoms of burnout after psilocybin administration (for patients randomized to psilocybin or who receive open-label psilocybin) at 1 week, 4 weeks, 8 weeks, 12 weeks, and 6 months.
- Another secondary endpoint will assess symptoms of post-traumatic stress using the PCL5, measured at 1 week and 4 weeks after the medication session.
 We expect at least 50% of participants treated with psilocybin to show a reduction in PCL5 scores by at least 10 points (the clinically meaningful threshold for improvement).
- Assess symptoms of post-traumatic stress using the PCL5 after psilocybin administration (for patients randomized to psilocybin or who receive openlabel psilocybin) at 1 week, 4 weeks, 8 weeks, 12 weeks, and 6 months.
- A 10% or less difference in the rate of adverse events between the treatment and control arms at all study visits.

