- j. Must provide a contact (relative, spouse, close friend, or other caregiver) who is willing and able to be reached by the Clinical Investigators in the event of a participant becoming suicidal.
- k. Must have a negative pregnancy test at study entry and prior to each medication dosing session if able to bear children and must agree to use adequate birth control.
- Are willing to commit to preparation sessions, medication dosing sessions, integration sessions, to complete evaluation instruments and commit to be contacted for all necessary telephone contacts.

4.2. Exclusion Criteria.

- a. Personal or immediate family history of schizophrenia, bipolar affective disorder, delusion disorder, paranoid disorder, or schizoaffective disorder.
- b. Suicidal ideation with a C-SSRS > 3
- c. Current substance abuse disorder (except in the case of mild alcohol use)
- d. Neuroleptic and SSRI medications that cannot be tapered and discontinued in conjunction with the participant's prescribing physician.
- e. Unstable neurological or medical condition; history of seizure, chronic/severe headaches.
- f. Positive urine pregnancy test at the time of screening
- g. Any unstable medical condition that my render study procedures unsafe based on the medical history performed as part of the screening procedures, including active cardiac medical issues such as ongoing angina, uncontrolled hypertension, or recent cardiac ischemia requiring medical attention (within the past 3 months
- h. Any use of psychedelic drugs within the prior 12 months.
- i. Use of tramadol, due to the potential for serotonin syndrome with concomitant use of

Page 23 Version 1.16, July 18, 2022

psilocybin.

- j. Allergy to niacin (N.B. the investigators will inform participants that flushing, redness, tingling, and headache are normal side effects that do not predict anaphylaxis, which although reported is extremely rare).
- k. Individuals who are on MOAI (monoamine oxidase inhibitors) or who have a known sensitivity to the drug or its metabolites. Psilocybin is contraindicated in medications that are known UGT (UDP-glucuronosyltransferase) enzymemodulators. The concurrent use of SSRI/SNRI meds is assumed to be contraindicated due to the potential to increase the risk of serotonin syndrome and/or to attenuate the binding of psilocin to the HT2A receptor.

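### The open-label schedule marks only the C-SSRS at Day 180', which contradicts the 6-month MADRS, burnout and PCL5 endpoints for open-label recipients

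*Combined protocol and SAP*

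**What the plan says.** **Endpoints (section 2.3.2).** Three secondary endpoints follow patients after psilocybin, whether it was randomized or open-label. One uses the MADRS. The other two read "Assess symptoms of burnout after psilocybin administration" and "Assess symptoms of post-traumatic stress using the PCL5 after psilocybin administration". All three are timed "at 1 week, 4 weeks, 8 weeks, 12 weeks, and 6 months".

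**Open-label schedule (section 6.3).** The table headed "Schedule for Activities during Open Label Psilocybin Phase" has ten day columns, from -1' to 180'. Its footnote treats the last visit as planned: "Note that V13, V14, V15, and V16 are likely to be video or remote visits". At Day 180' only the C-SSRS row carries a mark. There is no MAIA2 row and no pregnancy-test row, but a urine screen is marked at Day 0'.

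**Follow-up of participants randomized to psilocybin (section 3.1).** Day 180 (V10) marks MADRS, Beck, SFI, PCL5, likelihood to leave job, AAQII, MAIA2, C-SSRS and adverse events.

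**Related text.**
- Section 6.2.5 gives a therapist phone or video call at 3 and 6 months after psilocybin. It says that this allows for open-label recipients, and that participants complete measures online. It does not name the instruments.
- Sections 6.1 and 6.3 say: "Participants will be re-assessed on all study measures following the same schedule of the randomized phase".
- Section 4.1(k) says: "Must have a negative pregnancy test at study entry and prior to each medication dosing session", for those able to bear children.

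**The concern.** Staff normally work from the schedule of activities. Anyone who follows the open-label table at V16 would administer the C-SSRS and nothing else. Three stated secondary endpoints would then lack their 6-month value in the open-label recipients, while the randomized psilocybin arm would have it. The two groups exposed to psilocybin would have different follow-up, and the protocol gives no reason for the difference. A 6-month rating that is not taken cannot be recovered later.

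**Working it through.** The plan gives no figure to reproduce here. The check compares the schedule with the endpoints and then sizes the possible loss.

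**1. Are the blanks real?** Each measure row in the open-label table has ten cells for ten study days, so no row has shifted.
- C-SSRS: 10 of 10 visits.
- Adverse events: 9 of 10, all but Day 180'.
- MADRS, Beck, SFI and PCL5: 8 of 10 each, all but Day 0' and Day 180'.
- AAQII: marked up to Day 84' and blank at Day 180'.

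The table is split by a page break. The MADRS, Beck, SFI and PCL5 rows stand before it and the C-SSRS row after it. The AAQII and adverse-event rows stand in the same part as the C-SSRS row and are also blank at Day 180'. The visit-number row, before the break, includes V16. Extraction error is therefore unlikely, but the original table should be looked at.

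**2. Endpoint times against the schedules.**

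| Time in 2.3.2 | Open-label day (visit) | MADRS, SFI, PCL5 |
|---|---|---|
| 1 week | 7' (V10) | marked |
| 4 weeks | 28' (V13) | marked |
| 8 weeks | 56' (V14) | marked |
| 12 weeks | 84' (V15) | marked |
| 6 months | 180' (V16) | blank |
| 6 months, randomized psilocybin arm | 180 (V10 in the 3.1 table) | marked |

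Four of the five times agree. Only the 6-month time fails.

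**3. Does other text fill the gap?**
- The re-assessment sentence in 6.3 points to the schedule of the randomized phase. The table with that title ends at Day 28, and the Day 180 table is titled for participants randomized to psilocybin. Section 6.3 also directs the reader to the very table that has the gap.
- The 6-month contact in 6.2.5 could supply SFI and PCL5, which section 3.1.2 lists as self-report. It does not clearly supply the MADRS, which 2.3.1 and 3.1.1 class as clinician-administered. Section 3.1.4 describes a blinded study rater for such measures, whereas the 6.2.5 caller is a therapist who treated the participant.
- Section 3.1.2 also limits the SFI to baseline and 4 weeks, which conflicts with the burnout times in 2.3.2.

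**4. Size.** The niacin arm is 15 (sections 3.1.4 and 6.1). Let u be open-label uptake, which the documents do not give. The number with 6-month data if V16 were complete is n = 15 + 15u, against 15 if every open-label recipient were missed. At equal SD and before dropout, the confidence interval widens by √(n/15).

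| Assumed u | n | √(n/15) |
|---|---|---|
| 0% | 15 | 1.00 |
| 50% | 22.5 | 1.22 |
| 80% | 27 | 1.34 |
| 100% | 30 | 1.41 |

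**The case against.** The strongest reply is that the text already provides for these data. Section 6.2.5 plans a 6-month contact that expressly covers open-label recipients, and 6.3 promises re-assessment on all measures. A reader of the table alone might infer that the 6-month data would certainly not be collected. The documents do not support that. What stands is a conflict between table and text that leaves collection uncertain, most of all for the MADRS.

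A reader might also infer that the endpoints require 6-month adverse-event data from open-label recipients. They do not. The adverse-event endpoint compares the treatment and control arms and names neither open-label recipients nor 6 months, and section 8.2 describes weekly review only to week 4. The blank adverse-event cell is a mismatch with the randomized psilocybin arm's Day 180 visit and breaches no endpoint.

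The missing pregnancy row might be taken to mean that no test is required before open-label dosing. Sections 4.1(k) and 6.2.3 already require one, and 6.3 calls for nearly identical procedures. The Day 0' urine screen may or may not be that test, so only the labelling is open.

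Finally, the open-label phase is optional, its data are described as descriptive or secondary, and no 6-month endpoint is in the testing hierarchy of section 9.2. All of that is right. It limits the consequence but does not remove the contradiction with three named endpoints.

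**Conclusion.** The contradiction is real and confined to one column: Day 180' in the open-label table conflicts with the 6-month MADRS, burnout and PCL5 endpoints in 2.3.2 and differs from Day 180 in the randomized psilocybin arm. If staff follow the table, the 6-month MADRS would probably be missed in open-label recipients; SFI and PCL5 might still arrive through the online measures.

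At most 15 niacin participants are affected, and that ceiling assumes that all of them take open-label psilocybin. At an assumed uptake of 50% to 100%, losing them would widen a 6-month interval by a factor of 1.22 to 1.41, at equal SD and before dropout. The week-4 primary analysis and the hierarchical tests are unaffected. The finding rests on the blanks being present in the original table.

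**What to change.** - In the open-label table, mark MADRS, SFI and PCL5 at Day 180' (V16), so that it agrees with 2.3.2.
- State in 6.2.5 who rates the 6-month MADRS and name the instruments completed online.
- Remove the conflict between the SFI timing in 3.1.2 and the burnout times in 2.3.2.
- For parity with the randomized psilocybin arm, also mark Beck, AAQII and adverse events at Day 180' and add a MAIA2 row with that visit marked. These additions rest on parity only: Beck is in no endpoint, AAQII is exploratory at 4 weeks, and MAIA2 is exploratory with no stated time.
- Reconcile the Day 0' urine-screen entry with the pregnancy-test requirement in 4.1(k) and 6.2.3, so that the table shows which test is meant.

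The cost is a table correction and a few sentences, plus a little more assessment time, including rater time for the MADRS, at a remote visit that is already planned.
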